7.2. Subject Exclusion Criteria

Patients who meet any of the following criteria will not be eligible to participate:

1. Total fasting TG >500 mg/dL (5.6 mmol/L) at Week -5 (Visit S1).

Note: A single repeat of TG may be completed prior to initiation of the single-blind Run-in Period. For those patients who have a repeat TG, the repeat value will be used to determine eligibility.
2. Renal dysfunction or a glomerulonephropathy defined as either nephritic or nephrotic syndrome, including estimated glomerular filtration rate (eGFR; using central laboratory determined Modification of Diet in Renal Disease [MDRD] formula) <30 mL/min/1.73 m² at Week -5 (Visit S1).

Note: A single repeat of eGFR may be completed prior to randomization. For those patients who have a repeat eGFR, the repeat value will be used to determine eligibility.
3. Forms of CVD that include any of the following:
 - a. Recent (within 90 days prior to or during screening) acute CVD events including, but not only transient ischemic attack (TIA), MI, coronary revascularization, peripheral arterial revascularization, ischemic stroke, carotid endarterectomy, carotid stenting,
 - b. Recent (within 90 days of screening) unstable or symptomatic cardiac arrhythmia (including any associated medication changes). Patients with stable well-controlled atrial arrhythmias will be allowed to participate in the study.

- c. Patients with implantable pacemakers or automatic implantable cardioverter defibrillators may be considered if deemed by the investigator to be stable for greater than 90 days prior to screening,
- d. New York Heart Association (NYHA) Functional Classification Class IV heart failure,
- e. Uncontrolled hypertension, defined as mean sitting systolic blood pressure (SBP) ≥ 180 mmHg and/or diastolic blood pressure (DBP) ≥ 110 mmHg,

Note: At the discretion of the investigator, BP medications can be adjusted and/or additional assessment of BP may be completed prior to randomization, with the repeat assessment value used to determine eligibility. Alternatively, patients can be rescreened if BP status has changed.

- f. Planned coronary revascularization (patient may rescreen 3 months post-procedure).
4. HbA_{1c} $\geq 10\%$ at Week -5 (Visit S1).

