15.8.1. Adverse Events of Special Interest (AESI)

All AESI will be identified and evaluated by routine safety monitoring of AEs and laboratory values (where appropriate) and will be summarized by severity and relationship to IMP for each treatment group.

The following are considered AESI categories for this study:

- Hepatic Safety, including liver-associated enzymes, TB, and any Hy's law cases ($\geq 3 \times$ ULN for either ALT or AST, with accompanying TB $>2 \times$ ULN in the setting of no known other cause)
- Musculoskeletal Safety, including CK
- Diabetes and Glycemia, including new onset of diabetes and worsening of diabetes
- Hypoglycemia Associated with Metabolic Acidosis
- Renal Impairment, including lab measures of renal function
- Neurocognitive Events
- Atrial Fibrillation
- Tendon Rupture/Tendinopathy. The TRAC will adjudicate events of tendon rupture per the TRIAC, and adjudicated events will be summarized.
- Malignancies

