7.4. Diabetes Related Definitions

7.4.1. Baseline Glycemic Status

Analyses of diabetes and related biomarkers are conducted with specific subsets of study population based on the baseline glycemic status defined in Table 1.

- For efficacy analyses of new-onset type 2 diabetes (conducted in the study population with No Diabetes at baseline), and related biomarkers HbA1c and fasting glucose, the FAS (or PPS for sensitivity analyses) is used with subpopulations defined according to the baseline glycemic status.
- For safety analyses of AESIs of *new-onset diabetes* (conducted in the study population with No Diabetes at baseline), and *worsening hyperglycemia* (Diabetes at baseline), and related safety laboratory measures including HbA1c and fasting glucose, the SAS is used with subpopulations defined according to the baseline glycemic status.

Table 1: Baseline Glycemic Status

Status	Definition
Diabetes	Meeting 1 or more of the following criteria at baseline captured by information recorded prior to Day 1: 
 • Medical history or adverse events indicating diabetes as defined in the Diabetes Committee Charter (attached as Appendix 8) • Prior glucose-lowering medication as defined by the Diabetes Committee Charter (attached as Appendix 8) • HbA_{1C} measurement $\geq 6.5\%$ • Two or more measurements of fasting glucose ≥ 126 mg/dL (7.0 mmol/L)
Inadequately Controlled (IC) Diabetes	With Diabetes and a HbA _{1C} of 7% or greater at baseline.
No Diabetes	Not meeting any of the criteria for Diabetes at baseline.
Prediabetes	No Diabetes at baseline, and with: 
 • HbA_{1C} measurement of $\geq 5.7\%$ and $< 6.5\%$, OR • 1 or more measurements of fasting glucose ≥ 100 mg/dL (5.6 mmol/L), but not more than 1 value of fasting glucose ≥ 126 mg/dL (7.0 mmol/L).
Normoglycemia	No Diabetes, and not meeting the criteria for Prediabetes at baseline.

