16.1.2. Adverse Events of Special Interest

 AESIs will be identified by specified MedDRA PTs, or the related laboratory criteria if applicable. See [Appendix 7](#) for the list of AESIs and their definitions. These events will be summarized by AESI category, laboratory criteria met (if applicable), and PTs.

The NODM AESI is applicable only for patients with baseline glycemic status ([Section 7.4](#)) of No Diabetes at baseline. As an AESI vs. an efficacy endpoint, NODM includes a broader definition of NODM with patients who meet one of the following conditions:

- patients with verified NODM as determined by the DC ([Section 7.4.3](#)), or
- patients who initiated a diabetes medication after first dose of IMP ([Appendix 8](#)), or
- patients meeting the laboratory criteria for NODM as in [Appendix 7](#), or
- patients with selected AE preferred terms (see list of preferred terms for ‘NODM’ in [Appendix 7](#)).

Worsening Hyperglycemia AESI is applicable to patients with baseline glycemic status of Diabetes based on adverse event preferred terms as described in [Appendix 7](#).

See [Appendix 7](#) for the list of AESIs and their definitions. AESIs will be identified by specified MedDRA PTs, and/or the related laboratory criteria if applicable. These events will be summarized by treatment group, and by AESI category, laboratory criteria met, and PTs.

Malignancy AESI will be summarized by Standardised MedDRA Queries (SMQs) and PTs as described in [Appendix 7](#).

Tendon rupture will be summarized for events that are positively adjudicated according to the TRAC Charter. All potential tendon ruptures that were reviewed by the TRAC will be presented in a listing.

For AEs considered to be muscle related by the Investigator, additional information is collected on the *Muscle Related Adverse Event Complementary* CRF including the primary cause, locations, and whether the AE is unilateral or bilateral.

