16.3. Safety Laboratory Evaluations

The list of central laboratory assessments to be included in the outputs is included in the Table 4 of the Protocol (Section 12.1.6.1) and includes H_bA_{1c}. Urinalysis is not quantitative, and coagulation is measured at selected patients/visits only, and these will not be summarized.

In addition, eGFR will be calculated using the formula: $186 \times (\text{creatinine}/88.4)^{-1.154} \times (\text{age})^{-0.203} \times (0.742 \text{ if female}) \times (1.210 \text{ if Black})$, where creatinine is in μmol/L. Blood urea nitrogen (BUN)/creatinine ratio (BUN/Creatinine ratio) will also be calculated.

Summaries for all lab results will be included for the below analyses:

- Observed and change/percent change from baseline by analysis visit for hematology and blood chemistry measurements.
- Creatinine and eGFR will be summarized by treatment group and by baseline eGFR categories (<30, 30 to <60, 60 to <90, and ≥90 mL/min/1.73m²).
- Fasting glucose and HbA_{1c} will be summarized by baseline glycemic status, and by treatment group.

[figure not shown]
The analyses for shift tables from baseline to the worst post-baseline category or value are presented in Table 2. Note that for fasting glucose and HbA_{1c} the analyses will be by baseline glycemic status.

Table 2: Analyses for Shift Tables of Laboratory Parameters

Parameter	Categories (From Better to Worse)
Fasting glucose (by baseline glycemic status)	<51 mg/dL ≥51 to <100 mg/dL ≥100 to <126 mg/dL ≥126 mg/dL
H _b A _{1c} (by baseline glycemic status)	<5.7% ≥5.7% and <6.5% ≥6.5 to <7% ≥7%
Alanine aminotransferase (ALT)	Normal, High (> ULN)
Aspartate aminotransferase (AST)	Normal, High (> ULN)
eGFR	≥90 mL/min/1.73m ² ≥60 to <90 mL/min/1.73m ² ≥30 to <60 mL/min/1.73m ² <30 mL/min/1.73m ²
Uric acid (UA)	Low/Normal (combined) High (> 5.7 mg/dL for female, >7.0 mg/dL for male)

Lab abnormalities associated with AESIs are listed in Appendix 7 and will be summarized with the AESIs. In addition, for evaluation of potential Hy’s Law cases, a pairwise scatterplot will be created with the maximum (peak) post-baseline values of ALT or AST as multiples of the ULN, against the concomitant TB (also multiples of the ULN).

Other lab abnormalities of selected parameters are presented in Table 3 and the number of patients meeting each criterion will be summarized by treatment group.

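### The HbA1c shift table in SAP Table 2 ends at an open category of 7% and above, so it cannot show worsening in patients with Inadequately Controlled Diabetes

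*SAP*

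**What the plan says.** - **The shift table.** SAP Section 16.3 states: "The analyses for shift tables from baseline to the worst post-baseline category or value are presented in Table 2". It adds that HbA1c and fasting glucose are tabulated by baseline glycemic status. The HbA1c categories are "<5.7% ≥5.7% and <6.5% ≥6.5 to <7% ≥7" (percent) and the fasting-glucose categories are "<51 mg/dL ≥51 to <100 mg/dL ≥100 to <126 mg/dL ≥126 mg/dL". In both, the final category is open-ended and is the worst.
- **The stratum.** SAP Section 7.4.1, Table 1, defines Inadequately Controlled Diabetes as diabetes with HbA1c "of 7% or greater at baseline". The definition has no glucose condition.
- **The safety interest.** Protocol Section 15.8.1 lists as an AESI category "Diabetes and Glycemia, including new onset of diabetes and worsening of diabetes", and says AESIs are assessed from adverse events and, where suitable, laboratory values. SAP Section 7.4.1 names HbA1c and fasting glucose as the laboratory measures that go with the two diabetes AESIs.
- **How the worsening AESI is counted.** SAP Section 16.1.2: "Worsening Hyperglycemia AESI is applicable to patients with baseline glycemic status of Diabetes based on adverse event preferred terms".

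**The concern.** A shift table exists to show how many individual patients moved to a worse category and whether the arms differ. When the worst category begins at the value that defines a stratum, nobody in that stratum can move. Here the affected stratum is the one with the poorest glycemic control at entry, and SAP Section 15.3.4 makes it the main subgroup for the HbA1c efficacy analysis. Its row will show no worsening whatever the drug does, and a reader of the study report could take an empty cell for evidence of no deterioration. At stake is the usefulness of one descriptive safety table. No test, estimate or AESI count depends on it.

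**Working it through.** The plan states no figure to reproduce. The check applies the Table 2 cut-points directly.

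**Inputs**
- HbA1c cut-points 5.7, 6.5 and 7.0%; glucose cut-points 51, 100 and 126 mg/dL (SAP Table 2).
- Inadequately Controlled Diabetes: HbA1c of at least 7% at baseline (SAP Table 1).
- Entry limit: HbA1c of 10% or more at screening is excluded (Protocol Section 7.2).
- Baseline glucose averages the two most recent fasting results and is defined independently of HbA1c (SAP Section 7.2.3).

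**Rule.** Let c(v) be the number of cut-points at or below the value v, so c runs from 0 to 3. A worse shift needs c(worst post-baseline) > c(baseline).

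**HbA1c**
- For any baseline of 7% or more, c = 3, the maximum, so a worse shift is impossible.
- On a grid of 0.1-point steps from 5.0 to 12.9% (80 values), baselines 7.0 to 9.9% (30 values) give 30 × 80 = 2,400 baseline/post-baseline pairs and 0 worse shifts.
- Baselines 5.0 to 6.9% give 1,331 worse-shift pairs: 7 × 73 + 8 × 65 + 5 × 60 = 511 + 520 + 300. Diabetics who enter below 7% can therefore shift up.
- 7.1% to 9.9%, a rise of 2.8 points, is c = 3 to 3: no shift. 6.8% to 7.2%, a rise of 0.4 points, is c = 2 to 3: a shift.

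The result does not depend on whether Inadequately Controlled Diabetes gets its own panel. SAP Table 1 classes anyone with HbA1c of 6.5% or more as having diabetes, so the baseline row at 7% and above consists of these patients in either layout.

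**Fasting glucose**
- Baseline 126 or 180 mg/dL: c = 3, no worse shift possible.
- Baseline 110 or 125 mg/dL, later 150: c = 2 to 3, a worse shift.
- The documents give no glucose distribution for this stratum. Assuming a normal distribution, the share starting below 126 is Φ((126 − mean)/SD). For mean 170, SD 30: Φ(−1.47) = 0.07. For mean 140, SD 50: Φ(−0.28) = 0.39. Over means of 140 to 170 and SDs of 30 to 50, about 7% to 39% start below the ceiling and 61% to 93% at it.

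**What the other outputs give for this stratum**
- SAP Sections 15.3.4 and 16.3: HbA1c values and changes by visit, arm and glycemic status, with between-arm differences and 95% CIs in the efficacy section. These are group-level results.
- SAP Section 8.6: quartiles, minimum and maximum alongside means. These describe spread but do not count patients who worsened.
- SAP Section 16.1.2: AESI counts from adverse event terms.
- SAP Appendix 10: a patient listing, not a count by arm. Its HbA1c criterion is above 10%, so a rise to 9.9% does not trigger it. Its fasting-glucose criterion, above 126 mg/dL, does not separate stable from worsening patients already above that value.

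**The case against.** A reader might infer that worsening of diabetes, as an AESI, must come out as zero in both arms. The documents do not support that: the AESI is counted from adverse event terms in all patients with baseline diabetes, and Table 2 plays no part. Nor does every patient with Inadequately Controlled Diabetes start at the top of both tables, since the definition does not mention glucose.

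The strongest case on the other side is that real harm would be seen elsewhere. HbA1c is not among the laboratory values masked under Protocol Section 8.3. Protocol Sections 13.1.3 and 13.2.3 give a clinically significant rise, or one that needs intervention, a route to an adverse event record. SAP Section 13.2 summarizes changes in antidiabetic medication by glycemic status. A uniform rise would show in the change-from-baseline analysis: with an assumed rise of 0.3 points, SD 0.7 and 200 patients per arm, SE = 0.7 × √(2/200) = 0.07 and z = 0.3/0.07 ≈ 4.3. The planned upper quartile would move too. This stands, and it limits the point to how individual deterioration is reported.

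It does not make the table informative. A group average can stay flat while some patients improve and others worsen, and quartiles do not give the number who rose by a stated amount. The adverse event route depends on investigator judgment or action.

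The contents of SAP Table 3, Appendix 7, Section 15.4.4 (additional diabetes analyses) and Section 15.6.2 (responder analyses) are not in the available text. Any of them might hold a categorical HbA1c analysis, so no absence is inferred from them. The ceiling in Table 2 holds regardless.

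**Conclusion.** The point holds for Table 2 itself. In patients with baseline HbA1c of 7% or more, the count of worse HbA1c shifts is exactly zero in both arms by construction, with no assumption needed. In the glucose table the same is true only of patients already at 126 mg/dL or more; how many patients with Inadequately Controlled Diabetes that covers cannot be read from the documents, and the 61% to 93% above rests on an assumed distribution.

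It would go too far to say that an imbalance in deterioration would be reported as none. The AESI count and the stratified change summaries remain, and a general rise would be visible. What is missing, among the outputs that can be read, is a by-arm count of individual patients in this stratum whose HbA1c worsened. This is a limited reporting gap in a section with no planned between-arm tests unless specified, but it is worth closing because the table is already planned and the repair is small.

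**What to change.** Before unblinding:

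1. In SAP Table 2, split the open top categories. For example, report HbA1c as 7 to <8, 8 to <9, 9 to <10 and ≥10%, and fasting glucose as 126 to <200 and ≥200 mg/dL. These are reporting cut-points only; they imply no treatment threshold and change no patient management.
2. Check SAP Table 3, Appendix 7 and Section 15.4.4. Unless one of them already provides it, add a descriptive count and percentage by arm of patients with diabetes at baseline who have a sustained HbA1c rise, for example at least 0.5 and at least 1.0 percentage points above baseline at two consecutive visits. State the denominator.

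HbA1c is already measured at Months 3, 6 and 12 and every 6 months thereafter, so no new data are needed, and the primary and key secondary testing is untouched. The cost is some programming and a slightly larger table with sparser cells. Fixing the cut-points before unblinding avoids choosing them after the results are seen; if added later, the output should be marked ad hoc, as SAP Section 5.3 provides.

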12.1.6.3.1. Monitoring and Management of Elevated Liver Function Tests

If at any time after randomization a patient experiences a new ALT and/or AST >3 × ULN, the patient will undergo repeat confirmatory liver function test (LFT) assessment as soon as is reasonably possible, preferably within 3 to 7 days of the laboratory result becoming available.

Repeat LFT assessment will include: 1) measurement of ALT, AST, alkaline phosphatase, total and direct bilirubin, prothrombin time (PT)/international normalized ratio (INR), eosinophil count, CK; 2) history of concomitant medication use; 3) history of exposure to environmental chemical agents, including ethanol; and 4) query for related symptoms. Additionally, further

testing such as antihepatitis A virus (total), HBsAg (confirmation of screening measurement), HCV (confirmation of screening measurement), and anti-cytomegalovirus/immunoglobulin M, Epstein-Barr, liver ultrasound or magnetic resonance imaging (MRI) scanning may be warranted to rule out additional pathology depending on clinical presentation and should be discussed with the Sponsor personnel or the authorized Medical Monitor. Although samples will be collected, some repeat LFT parameters may not be measured until elevation is confirmed.

- If repeat LFT assessment confirms ALT and/or AST $>3 \times$ ULN but $\leq 5 \times$ ULN, consideration should be given to administering no further doses of IMP. At the investigator's discretion, IMP may be interrupted and the patient rechallenged with IMP after LFTs have returned to baseline levels.
- If repeat LFT assessment confirms ALT and/or AST $>5 \times$ ULN and no alternative reason for elevation is identified, patient should be discontinued IMP treatment, but will be asked to continue to be followed for safety using the protocol-specified visit schedule (see Appendix 1). At the investigator's discretion, IMP may be interrupted and the patient rechallenged with IMP after LFTs have returned to baseline levels.
- If repeat LFT assessment confirms ALT and/or AST $>3 \times$ ULN in addition to any of the following and no alternative reason for elevation is identified, patient should be discontinued IMP treatment, the patient should be given no further IMP treatment, but should continue to be followed for safety using the protocol-specified visit schedule (see Appendix 1):
 - TB $>2 \times$ ULN
 - INR $>1.5 \times$ ULN (unless the patient is on stable dose of anticoagulation medication)

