7.2.4. Analysis Visit Windows

For data analysis purpose, unless otherwise specified, study assessments will be assigned to analysis visits based on the Study Day (Section 7.2.2), and analysis visit windows specified in Appendix 3.

For lipids parameters (LDL-C, non-HDL-C, TC, HDL-C, TG) and hs-CRP, the *date of randomization* will be used as the start date to determine the analysis visit windows. For hs-CRP only, the end-of-study (EOS) measurement is defined as the last measurement taken for the patient.

In cases where multiple assessments fall into the same analysis visit, and only one is used for analysis, it is selected based on the following rules.

- The assessment closest to the target (nominal visit) date will be used.
- If there are ties, the assessment after the target date will be used.
- If multiple values are available with the same date and time, the assessment with larger laboratory accession number (LBREFID) will be used.

Note that unscheduled visits are treated the same way as scheduled visits.

Nominal visits (e.g., S1, S2, T1, etc, see Appendix 1) may be used in listings as appropriate.

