Patients with potentially clinically significant laboratory abnormalities (Appendix 10) will be listed. For a given parameter (or group of parameters as indicated), all values from the patient will be included in the listing if any value meets the criteria.

As a result of the pandemic, local laboratory may be used for safety labs at the investigators’ discretion. The local lab data are reviewed and evaluated by the investigators for any abnormalities and adverse event reporting as applicable. Due to the diverse use of units and

variation in laboratory normal ranges, the local lab data are not used in the statistical analyses. All local laboratory measurements will be listed with the associated reference ranges if available. Abnormal laboratory results of ALT and/or AST $>3 \times$ ULN, TB $>2 \times$ ULN or CK $>5 \times$ ULN based on the non-central laboratory reference ranges (when available) will be noted in the listing.

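### The SAP's Hy's Law plot can place a patient outside the Hy's Law region when both limits are first met on a sample later than the ALT/AST peak

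*SAP*

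**What the plan says.** SAP 16.3 announces that "for evaluation of potential Hy’s Law cases, a pairwise scatterplot will be created". The plotted quantities are "the maximum (peak) post-baseline values of ALT or AST as multiples of the ULN, against the concomitant TB", with bilirubin also as a multiple of ULN. The section gives neither a definition of 'concomitant' nor a rule for two samples that share the same peak.

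Protocol 15.8.1 describes a Hy's Law case as at least 3 x ULN "for either ALT or AST, with accompanying TB" above 2 x ULN, with no other known cause. It gives no time window for 'accompanying'.

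Protocol 12.1.6.3.1 requires a repeat liver panel after any new ALT or AST above 3 x ULN, "preferably within 3 to 7 days of the laboratory result becoming available". The repeat includes "measurement of ALT, AST, alkaline phosphatase, total and direct bilirubin". One of the rules judged on that repeat is ALT or AST above 3 x ULN "in addition to any of the following and no alternative reason for elevation is identified"; bilirubin above 2 x ULN is the first item on its list.

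Two other SAP provisions bear on the point. On visit assignment, SAP 7.2.4 says "Note that unscheduled visits are treated the same way as scheduled visits". On potentially clinically significant abnormalities, SAP 16.3 says "all values from the patient will be included in the listing if any value meets the criteria"; Appendix 10 lists ALT, AST and total bilirubin together, ordered by timepoint.

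**The concern.** The horizontal value is a patient-level maximum. The vertical value is whatever bilirubin went with that maximum. It is neither the patient's highest bilirubin nor the bilirubin on a sample that meets both limits. The protocol, by contrast, re-measures ALT, AST and bilirubin on a repeat sample and judges the combination there. If the transaminase has fallen by then but is still at or above 3 x ULN, and bilirubin has passed 2 x ULN, the repeat is the sample that qualifies. The plot ignores it because it is not the peak.

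At stake is whether the one figure designated for Hy's Law evaluation shows every patient who meets the laboratory part of the definition. Hepatic safety heads the AESI list in protocol 15.8.1, and protocol 4.2.2 names liver as a target organ in rats and monkeys. A reader of the figure will look at the upper-right quadrant and may look no further.

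**Working it through.** The plan states no figure to reproduce, so the check applies the plotting rule to constructed patients.

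**Inputs.** Horizontal axis: maximum post-baseline ALT or AST (SAP 16.3). Vertical axis: bilirubin on that same sample (the same-sample reading of 'concomitant'; an assumption, since the SAP leaves the term open). Region: ALT or AST >= 3 and bilirubin > 2, in multiples of ULN (protocol 15.8.1). Listing trigger: ALT > 3, AST > 3 or bilirubin > 2 (SAP Appendix 10). Repeat central samples are taken as eligible to be the peak: nothing in SAP 16.3 excludes them, and SAP 7.2.4 treats unscheduled visits like scheduled ones.

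**Rules compared.** (i) SAP plot: the pair (ALT, bilirubin) from the sample with the highest ALT. (ii) Does any single sample meet both limits? (iii) Peak ALT against peak bilirubin.

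Each illustrative patient has two samples, first then repeat, written as (ALT, bilirubin) in multiples of ULN. The values are assumed.

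| Patient | First | Repeat | (i) SAP plot | (ii) One sample meets both | (iii) Peak v peak |
|---|---|---|---|---|---|
| A: ALT falls, bilirubin rises | (6, 1.2) | (4, 2.5) | (6, 1.2), outside | yes, repeat | (6, 2.5), inside |
| B: ALT still rising | (4, 1.2) | (6, 2.5) | (6, 2.5), inside | yes, repeat | (6, 2.5), inside |
| C: both peak together | (6, 2.5) | (4, 1.5) | (6, 2.5), inside | yes, first | (6, 2.5), inside |
| D: ALT below 3 by the repeat | (6, 1.2) | (2.5, 2.5) | (6, 1.2), outside | no | (6, 2.5), inside |
| E: ALT tied | (5, 1.2) | (5, 2.5) | (5, 1.2) or (5, 2.5) | yes, repeat | (5, 2.5), inside |

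**Reading the table.**

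- A is the defect. The repeat has ALT 4 >= 3 and bilirubin 2.5 > 2, so it meets both limits, yet the plotted bilirubin is 1.2.
- B shows the condition. When the repeat holds the ALT peak, the plot is right.
- E turns on a tie rule that SAP 16.3 does not give.
- D shows the price of rule (iii): no single sample meets both limits, but the point lands inside the region.
- All five patients trigger the Appendix 10 listing, since each has an ALT above 3 on at least one sample.

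The protocol's repeat-sample rule uses ALT or AST above 3 x ULN, whereas its Hy's Law wording uses at least 3 x ULN. No value in the table sits at exactly 3, so the difference does not change any row.

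**The case against.** The strongest case against is that this is one supplementary figure. SAP 16.3 first says that AESI-related laboratory abnormalities are defined in Appendix 7 and summarised with the AESIs, and then adds the scatterplot. Protocol 15.8.1 places Hy's Law cases within the hepatic AESI category. The Appendix 10 listing would show patient A's repeat sample next to the first. All of this stands. Appendix 7 and the contents of SAP Table 3 are not in the supplied text, so whether the combined criterion is counted there cannot be checked, and their absence here is not a gap in the plan.

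It can also be said that 'concomitant' mirrors the protocol's 'accompanying', so the two documents do not contradict each other, and that a window wide enough to reach the repeat would capture patient A. That is fair. But if a window was intended, the SAP needs to state it, so an edit is needed on either reading.

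A third objection is that unwindowed peak against peak pairs values that may be years apart, since Appendix 1 of the protocol allows treatment up to about 57.5 months. This also stands, and it is why the fix separates the groups by symbol.

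A reader might infer more than the documents support, in three ways:

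- *That the trial would lose a Hy's Law case or understate a case rate.* No planned rate or bound is computed from the plot, and the listing keeps the patient visible.
- *That any patient whose bilirubin rises on the repeat is misplaced.* Patient B shows otherwise.
- *That the pattern will be common because scheduled chemistry is six-monthly after Month 6.* The visit interval does not say which sample holds which peak, and neither document describes the usual order of the two rises.

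**Conclusion.** The point holds in limited form. On the same-sample reading of 'concomitant', SAP 16.3 plots outside the Hy's Law region any patient who first meets both limits on a sample later than, and with a lower ALT or AST than, the peak sample, provided bilirubin on the peak sample is not above 2 x ULN. The repeat panel in protocol 12.1.6.3.1 is the obvious place for this to happen.

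The effect is confined to the figure. Its frequency is unknown, and no numerical effect on a safety conclusion is claimed. The conclusion assumes the same-sample reading and a central-laboratory repeat. Under SAP 16.3, local-laboratory results are listed but left out of the statistical analyses, so a local repeat would be absent from the plot whichever rule is used.

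The change is worth making because the figure exists to find such patients and the correction is cheap.

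**What to change.** In SAP 16.3, plot each patient's peak post-baseline ALT or AST against peak post-baseline total bilirubin, both as multiples of ULN and both taken over all central-laboratory samples, scheduled or not. Use separate symbols for:

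1. patients with ALT or AST >= 3 x ULN and bilirubin > 2 x ULN on the same sample at any time;
2. patients whose bilirubin > 2 x ULN follows the ALT or AST elevation within a pre-stated window. Thirty days is an example only; neither document gives a figure, and the sponsor would need to set it.

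Tabulate both groups by arm if Appendix 7 does not already do so.

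The cost is one or two sentences in the SAP and a small program change. No endpoint, alpha or patient procedure is affected. The downside is that some patients with unrelated, widely separated peaks will fall in the quadrant and need case review; the symbols show which ones they are.
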